## 1.0 Background and significance

The response to a wide variety of insults has been termed systemic inflammatory response syndrome (SIRS). SIRS is nonspecific and develops following a severe physiologic stress or insult, such as infection, trauma, surgery, pancreatitis, or burn. At least two SIRS criteria coupled with a known or suspected infection is termed “sepsis.” In a prospective survey of adult patients admitted to a tertiary care center, 68% of admissions met SIRS criteria, and 26% developed sepsis (SIRS due to an infection) (7). Hospital death associated with severe sepsis ranges from 18% to 28% in adults (8). Sepsis remains the leading cause of death in adult surgical ICU patients(9).

Clinical data are often unreliable in distinguishing between patients with sepsis (defined as SIRS with a known or suspected infection) and those with SIRS secondary to a cause other than infection. Trauma is frequently associated with SIRS (10), and, in the US, 5.7% of patients admitted after vehicular trauma develop an infection (9). Followed by evidence based management, early detection of infection after trauma could decrease complications and death due to sepsis (11). Overdiagnosis of infection and associated unnecessary use of antibiotic drugs is believed to promote antibiotic resistance and complications related to antibiotic exposure, such as morbidity associated with hospital acquired *C. difficile colitis*.

Analyses of some biomarkers is available and some may be useful for prompt diagnosis of infections, including systemic infections like sepsis. However, they are insufficient for monitoring infection progress to more severe forms like sepsis. WBC and absolute neutrophil count are inexpensive laboratory tests, but lack adequate sensitivity and specificity to detect serious infections (12). C-reactive protein (CRP) is an inexpensive test, but does not detect severe infections early (13). Procalcitonin (PCT) may be more specific than CRP in response to bacterial infections(14, 15), but is an expensive test, not commonly available in US clinical laboratories, and specificity is confounded in postoperative, burn, trauma, pancreatitis, vasculitis, and other non-infectious conditions that cause SIRS (13).

[figure not shown]
[figure not shown]

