For critically ill patients admitted to an ICU, the mean overall nosocomial infection rate is 6 to 18% (29, 30, 40). The incidence rate of infection could be greater for all surgical ICU patients. The infection rate in the previous proof-of-concept study was 50% using the same population and inclusion/exclusion criteria; this assumption of equal proportions of prospectively enrolled infected and uninfected subjects will be used in the sample size calculations which follow. Data collected to date indicate that a sustained change in BDV of 1.0‰ or more correlates with the presence of infection when the subject is used as his-her control. The average intra subject standard deviation (SD) across time points in critically ill adult subjects previously studied was 0.95‰, regardless of the underlying medical conditions. The inter subject SD is expected to be 1.0‰ at most. Using the BDV measurements during the breath sample monitoring period (breath sample assessments every 4 hours), the expected overall SD of the mean BDV measurements (across time points) is less than 1.0‰.

BDV sensitivity and specificity will be evaluated relative to PCT sensitivity and specificity according to non-inferiority hypothesis tests where a greater than 10% BDV disadvantage is to be ruled for both sensitivity and specificity relative to a less than 10% BDV disadvantage. The BDV sensitivity and specificity estimates will then be used to determine the positive predictive value (PPV) and negative predictive value (NPV) once the prevalence is known; prevalence surrogates can be used to apply the observed sensitivity and specificity to various ICU and CCU settings.

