## **6. Analysis Sets/Populations/Subgroups**

The first task is to demonstrate that there is a positive signal associated with the Canary test using the subject as their own control.

A per protocol analysis will be performed following EAC event reconciliation and subsequent database lock. The EAC will determine diagnostic truth by documenting severe sepsis or septic shock events as well as the onset and resolution dates.

Infection documentation will be reviewed by the EAC committee based on best clinical practices, using four categories:

- No suspicion of infection
- Inconclusive evidence of infection
- High suspicion of infection
- Overt infection

For sensitivity and specificity, non-inferiority testing will be performed to rule out a -10% disadvantage according to a one-sided 97.5% lower confidence limit for the BDV – PCT

difference; exact McNemar paired comparison tests will be performed to test BDV non-inferiority relative to PCT. Both endpoints must achieve statistical significance in order to achieve study success.

PPV and NPV will be computed as observed and for a range of possible infection prevalence (10%, 20%, 30%, and 40%). Results will be analyzed in the same manner as sensitivity and specificity.

BDV variations will be assessed using a two-sample t-test to compare the averaged (across time points) BDV between subjects who are diagnosed with a severe sepsis and sepsis shock vs. no severe sepsis or sepsis shock. Also a linear mixed effects model with subject specific random effects will be used to compare BDV measurements between the two diagnostic groups. This model will be also used to estimate the intra- and inter-subject variability of the BDV measurements. A paired t-test will be used to compare the BDV measurements prior to and after a diagnosis of infection or sepsis.

The definition of a positive BDV will be based on a 72-hour window without advance knowledge of the diagnosis. In the absence of clinical details supporting PCT operating characteristics (sensitivity, specificity), two PCT thresholds (0.5 and 2.0) will be evaluated but the 0.5 threshold is deemed to be primary for BDV comparison.

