Descriptive statistics will be generated for patient characteristics, demographics, and on-study events relating to subgroups (see Section 7.4). For continuous variables, descriptive statistics may include the number of subjects from whom data was used in the calculation, mean, standard deviation, median, minimum, and maximum; frequencies and percentages may be displayed for categorical data.

The predicate marker PCT sensitivity is estimated to be between 64-82% based on a recent review of the published literature (19); PCT sensitivity will be assumed to be 75% for sample size calculations. BDV sensitivity is expected to range between 80-90% based on the proof-of-concept study. The study is designed to have at least 80% power and one-sided 2.5% Type I error. A greater than 10% disadvantage for BDV vs PCT (null hypothesis) is to be tested against a less than 10% disadvantage for BDV vs PCT (alternative hypothesis). As shown in Table 1, this non-inferiority hypothesis can be tested with 97 documented infection events. The BDV advantage vs PCT resulting in a -10% one-sided 97.5% lower confidence bound (CB) is also displayed in Table 1; if the sensitivities are 76.5% for BDV vs 75% for PCT based on 97 pairs of infection events, then the one-sided 97.5% lower CB would be -10%, which would establish BDV non-inferiority relative to PCT.

Table 1: One-sided 97.5% Lower 97.5% Confidence Limit: Sensitivity Paired Differences (simulation)

	Power	N-I
Confidence level, 1-<math>\alpha</math> (one-sided)	0.975	0.975
Expected difference, <math>\pi_T - \pi_S, \Delta_1</math>	0.100	0.015
Proportion discordant, <math>\eta = \pi_{10} + \pi_{01}</math>	0.400	0.315
Proportion both yes, <math>\pi_{11}</math>	0.600	0.600
Lower limit for <math>\pi_T - \pi_S, LL</math>	-0.100	-0.100
Number of simulations	1000	1000
Random seed for simulations	123	123

Power (%)	89	51
n (number of pairs)	97	97

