The predicate marker PCT specificity is estimated to be between 56-78% based on a recent review of the published literature (19); PCT specificity will be assumed to be 65% for sample size calculations. BDV specificity is expected to range between 70-80% based on the proof-of-concept study. The study is designed to have at least 80% power and one-sided 2.5% Type I error. A greater than 10% disadvantage for BDV vs PCT (null hypothesis) is to be tested against a less than 10% disadvantage for BDV vs PCT (alternative hypothesis). As shown in Table 2, this non-inferiority hypothesis can also be tested with 97 documented non-infection events. The BDV advantage vs PCT resulting in a -10% one-sided 97.5% lower confidence bound (CB) is also displayed in Table 2; if the specificities are 66.5% for BDV vs 65% for PCT based on 97 pairs of non-infection events, then the one-sided 97.5% lower CB would be -10%, which would establish BDV non-inferiority relative to PCT. A 10% non-inferiority delta with respect to both sensitivity and specificity ensures that the performance of BDV is comparable to PCT, considering the difference in sampling methods and the potentially greater convenience of breath sampling for BDV.

Table 2: One-sided 97.5% Lower Confidence Limit: Specificity Paired Differences simulation)

	Power	N-I
Confidence level, 1-<math>\alpha</math> (one-sided)	0.975	0.975
Expected difference, <math>\pi_T - \pi_S, \Delta_1</math>	0.100	0.015
Proportion discordant, <math>\eta = \pi_{10} + \pi_{01}</math>	0.400	0.315
Proportion both yes, <math>\pi_{11}</math>	0.100	0.100
Lower limit for <math>\pi_T - \pi_S, LL</math>	-0.100	-0.100
Number of simulations	1000	1000
Random seed for simulations	123	123
Power (%)	87	52
n (number of pairs)	97	97

We will also categorize infections per respiratory and non-respiratory infections within our data analysis to determine if there is an impact on the breath delta value.

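### Study success is defined only relative to PCT, so if PCT fails to discriminate in this trial an uninformative BDV can meet both co-primaries; a floor on BDV's own discrimination would close the gap at almost no cost.

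*SAP*

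**What the plan says.** **The success rule.** SAP Section 5 sets up "non-inferiority hypothesis tests where a greater than 10% BDV disadvantage is to be ruled for both sensitivity and specificity", with PCT as the reference, and its two co-primary hypotheses are both BDV-versus-PCT comparisons. SAP Section 6 gives the decision bound, "non-inferiority testing will be performed to rule out a -10% disadvantage according to a one-sided 97.5% lower confidence limit" on the BDV minus PCT difference, and then the rule: "Both endpoints must achieve statistical significance in order to achieve study success". It says that the 10-point margin on both measures "ensures that the performance of BDV is comparable to PCT".

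**What is planned for PCT.** Section 6 takes PCT sensitivity as 64-82% and specificity as 56-78% from published literature, and plans on 75% and 65%. Two PCT thresholds are examined, introduced by "In the absence of clinical details supporting PCT operating characteristics (sensitivity, specificity"), with 0.5 as primary. Protocol Section 1.0 remarks that PCT "specificity is confounded in postoperative, burn, trauma, pancreatitis, vasculitis, and other non-infectious conditions that cause SIRS".

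**What is planned for BDV against diagnosis.** Section 6 calls a positive Canary signal the first task, without attaching a test or threshold. Sections 6 and 9 plan a two-sample t-test and a mixed model. Section 9 adds Fisher's exact test, kappa, and sensitivity, specificity, PPV and NPV with 95% intervals. The interim rule (under SAP Section 8) stops enrolment if no progressing subject had a positive BDV. None of these is a condition of success. Protocol Section 7.1 has a direct hypothesis, a 2.0‰ BDV difference between infected and non-infected subjects, but the SAP does not carry it into its success rule.

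**The concern.** A non-inferiority result supports the new test only if the comparator worked in the trial at hand. Here both co-primaries are differences from PCT, so if PCT carries no information in these patients, a BDV that also carries none has a true difference of zero on both measures whenever the two tests are positive equally often. That lies inside the alternative hypothesis. The rule could then declare success, although the SAP's stated overall objective is to show that BDV is a leading marker for infection. The interim rule gives little protection, because a test that is positive at random will usually be positive in at least one progressing subject.

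**Working it through.** **Inputs from SAP Section 6.** Margin 0.10; one-sided alpha 0.025; 97 infection and 97 non-infection pairs; planning values BDV 85/75 against PCT 75/65 (a difference of +0.10 on each measure); discordant proportion 0.400 (power column) and 0.315 (N-I column).

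**1. Reproduce the SAP's tables.** Let d be the true difference and η the discordant proportion. Power = Φ((d + 0.10)/√((η − d²)/97) − 1.96).
- d = 0.10, η = 0.400: SE = 0.0634; 0.20/0.0634 − 1.96 = 1.194; power 88.4% (SAP: 89% and 87%).
- d = 0.015, η = 0.315: SE = 0.0570; 0.115/0.0570 − 1.96 = 0.059; power 52.3% (SAP: 51% and 52%).

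The formula agrees with the SAP. The two groups are separate subjects or events, so joint power at the design values is about 0.884² = 0.78.

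**2. Both tests at chance, equal positive rate p.** Sensitivity is p and specificity is 1 − p for both tests, so d = 0. With independent tests η = 2p(1 − p).
- p = 0.50: SE = √(0.50/97) = 0.0718; 0.10/0.0718 − 1.96 = −0.567; each test passes 28.5% of the time; joint 0.285² = 8.1%.
- p = 0.90: SE = √(0.18/97) = 0.0431; 0.10/0.0431 − 1.96 = 0.361; each 64.1%; joint 41.1%.

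Simulation with a paired score (Tango) test is slightly more conservative at high p:

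| Positive rate of both tests | 50% | 70% | 80% | 85% | 90% |
|---|---|---|---|---|---|
| Both co-primaries met | 8% | 11% | 16% | 23% | 37% |

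The positive rates and the independence are assumptions; the documents give neither. Positive correlation between the tests raises the figures: at correlation 0.5 the score test gives about 24% (p = 0.50) and 69% (p = 0.90).

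**3. Unequal positive rates.** BDV positive in 50% and PCT in 60%: the sensitivity difference is −0.10, so that test passes 2.5% of the time. The specificity difference is +0.10 with η = 0.50, SE = √(0.49/97) = 0.0711, and 0.20/0.0711 − 1.96 = 0.854, so that test passes 80.3%. Joint: 0.025 × 0.803 = 2.0%. By simulation, gaps of 5 points give about 6-15%, 10 points about 2%, and 20 points about 0.04% or less.

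**4. How poor PCT must be.** For an uninformative BDV the two differences sum to 0 − (PCT index). If PCT's index is 0.20 or more, at least one difference is −0.10 or worse. That co-primary is then under its null, and joint success is at most the nominal 2.5%. At PCT 64/56 (index 0.64 + 0.56 − 1 = 0.20) and BDV 54/46 (index 0), both differences sit on the margin and joint success is about 0.025² = 0.06%. At PCT 55/55 and BDV 50/50 it is about 1.2%.

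**5. With a floor on BDV.** Require J − 1.96·√(se(1 − se)/97 + sp(1 − sp)/97) > 0, where J = se + sp − 1 for BDV. At J = 0 this passes about 2.5% of the time, so it caps joint success near that level. In the step 2 scenarios with independent tests, simulated false success is about 2.3% or less. At BDV 85/75, J = 0.60 and SE = √((0.1275 + 0.1875)/97) = 0.0570. J is more than 10 standard errors above 0, so the condition is met essentially always. Joint power is about 78% with and without it.

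**The case against.** **The headline range rests on equal positive rates.** Nothing ties the frequency of a BDV change above 1‰ to the frequency of PCT above 0.5, and a 10-point mismatch already brings the rule to about nominal alpha. This stands, so the 8-37% range should never be quoted without the unequal-rate figures.

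**The scenario is outside the SAP's own ranges.** PCT at chance with sensitivity of 64-82% would need specificity of 18-36%, against the SAP's 56-78%. This also stands. The protocol says that PCT specificity is confounded in some conditions; it does not say that PCT is uninformative.

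**Two stronger readings are tempting.**
- A reader might infer that the margins give away half of PCT's discrimination at 75/65 (0.20 of 0.40), or all of it at 64/56. Those points are the null boundary. BDV at 65/55 against 75/65, or 54/46 against 64/56, passes in under 0.1% of trials. By the SAP's own Tables 1 and 2, BDV must be observed about 1.5 points better than PCT on a measure for its lower bound to reach −10%. The SAP also gives two separate ranges, not a joint 64/56 point.
- A reader might take "In the absence of clinical details supporting PCT operating characteristics (sensitivity, specificity") as an admission that PCT does not work. In its sentence the clause explains why two thresholds are evaluated, and literature ranges follow it.

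**BDV is analysed against diagnosis anyway.** An uninformative BDV would probably be visible in the report, and the protocol (Section 3.0) describes a pilot for a later pivotal study with BDV not used clinically. This lowers the stakes. It does not close the gap, because none of those analyses binds the success decision.

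**Conclusion.** The point holds as a conditional weakness in the success rule. Success depends on PCT discriminating in this trial, and the rule neither checks that nor sets a floor for BDV. If PCT is uninformative, an uninformative BDV meets both co-primaries in about 8-37% of trials at equal positive rates of 50-90%, about 6-15% at a 5-point gap, about 2% at 10 points and about 0.04% at 20. These figures assume independent tests, 97 + 97 independent pairs and a score-based limit; positive correlation would raise them. If PCT's true index is 0.20 or more, the risk is at or below 2.5%. The documents therefore support a low-cost safeguard against comparator failure. They do not support a claim that the design is wrong at its planning values, or that a positive result would be meaningless.

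**What to change.** In SAP Sections 5 and 6, add a third success condition: the lower one-sided 97.5% confidence limit of BDV sensitivity + specificity − 1 must exceed 0. Report the same index with its confidence interval for PCT, as the check that the comparator discriminated in this trial.

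The cost is SAP wording and one more confidence limit from data already collected, with no extra subjects and no loss of joint power at the design values. All conditions must hold together, so no alpha adjustment is needed. The downside is one more condition for BDV to meet, which could matter only if BDV performs far below the expected 80-90% and 70-80% (index at least 0.80 + 0.70 − 1 = 0.50). For example, at BDV 65/55 the index is 0.20, its SE is √((0.2275 + 0.2475)/97) = 0.070, and the condition would be met about 81% of the time (0.20/0.070 − 1.96 = 0.90).

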### Objectives

To determine the following:

1. Evaluate the BDV as a marker of infections in critically ill subjects at risk of progressing to severe sepsis and septic shock;
2. To measure variation of BDV with time in critically ill ICU patients at risk of progressing to severe sepsis and septic shock among those who agree to participate as research subjects;
3. To determine the magnitude of change of BDV in subjects who subsequently progress to severe sepsis and septic shock;
4. To define variation of BDV in critically ill ICU subjects who do not progress to severe sepsis and septic shock.
5. Compare sensitivity and specificity, and positive and negative predictive value of the PCT marker with the BDV.

### Hypotheses

#### Co-Primary Endpoint 1

1. Null hypothesis: BDV sensitivity is more than 10% worse than PCT sensitivity for progression to severe sepsis and septic shock in critically ill adult ICU subjects
2. Alternative hypothesis: BDV sensitivity is less than 10% worse than PCT sensitivity for progression to severe sepsis and septic shock in critically ill adult ICU subjects

#### Co-Primary Endpoint 2

1. Null hypothesis: BDV specificity is more than 10% worse than PCT specificity for those not progressing to severe sepsis and septic shock in critically ill adult ICU subjects
2. Alternative hypothesis: BDV specificity is less than 10% worse than PCT specificity for those not progressing to severe sepsis and septic shock in critically ill adult ICU subjects.

#### Secondary Endpoint 1

1. Null hypothesis: the variability of BDV in critically ill adult ICU subjects does not change after clinical diagnosis of progression to severe sepsis and septic shock.
2. Alternative hypothesis: the variability of BDV in critically ill adult ICU subjects increases after clinical diagnosis of progression to severe sepsis and septic shock.

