## 2.0 Objectives

### 2.1 Primary objective

To define variation of BDV in critically ill adult subjects admitted to ICUs.

Hypothesis to be tested:

- Null hypothesis: BDV in critically ill adult ICU subjects is equal to BDV in non-infected adult ICU subjects.
- Alternative hypothesis: BDV in critically ill adult ICU subjects is different from BDV in non-infected adult ICU subjects.

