### 3.0 Study design and rationale

This is a multi-center prospective study to assess exhaled  $^{13}\text{CO}_2/^{12}\text{CO}_2$  BDV as an indicator of infection in critically ill adult ICU subjects. Critically ill adult ICU subjects who are not suspected of having an infection at the time of ICU admission will be enrolled as study subjects. Up to 100 Subjects will be enrolled from 8-10 centers across the United States.

This study is needed to determine the rate of infection detection of the Canary device. Logistic considerations include the definition of an infection and collection of data needed to diagnose infections consistent with the Centers for Disease Control (CDC) standards (16), and determination of onset timing of infection by clinical standards and by BDV. The BDV, as determined by the Canary™, will be retrospectively determined from exhaled breath samples, and will not be available or used clinically to establish or confirm the infection.

Effectiveness parameters will be estimated to determine the sample size required for the subsequent pivotal study. Parameters to be estimated include: timing of the infection onset, the lead time offered by various BDV thresholds, sensitivity of the BDV threshold, specificity of not reaching the BDV threshold, the receiver operating curve as a function of the BDV threshold, and the positive and negative predictive values based on hypothetical infection incidence. Models for infection outcome (Y/N) will be analyzed for the impact of clinical and on study covariates. The corresponding performance of a conventional best practices control (BPC) will be compared to determine if the Canary can identify infections earlier in the clinical course than BPC. Several time windows will be tested to determine the timing of and criteria for aligning a monitoring test result with BPC or clinical reference standard result. This pilot study will be used to formulate strategies to help control the Type I error (“false positive”) associated with multiple times when BDV could become positive. The pilot study will assess the robustness of the effectiveness outcomes across a broad spectrum of possible infection types.

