## **7.0 Data analysis and statistical considerations**

### **7.1 Sample size determination**

For trauma patients admitted to an ICU, the mean overall nosocomial infection rate is 6 to 18%. (9, 19, 20) The incidence rate of infection could be greater for all surgical ICU patients. Data collected to date indicate that a sustained decrease in BDV of 2.0‰ or more correlates with the onset of infection when the subject is used as his-her control. The average intra subject standard deviation (SD) across time points in 32 mechanically ventilated subjects previously studied was 1.16‰, regardless of the underlying medical conditions. The inter subject SD is expected to be 1.5‰ at most. Using the BDV measurements during the breath sample monitoring period (breath sample assessments every 4 hours), the expected overall SD of the mean BDV measurements (across time points) is less than 1.5‰.

Furthermore, during the monitoring period, the mean difference in the BDV between subjects who are diagnosed with a nosocomial infection and subjects not diagnosed with an infection is expected to be 2.0‰ or more (primary hypothesis). This difference will be considered to be the minimum difference with clinical importance.

Assuming that 5% of the subjects will have a confirmed nosocomial infection over the monitoring period and an overall standard deviation of 1.5‰, a total sample size of 100 subjects (5 infected and 95 non-infected) is required to detect a minimum clinically-important difference of 2.0‰ with at least 80% power at the two-sided 5% significance level.

If the actual rate of nosocomial infections is 10%, then the proposed total sample size of 100 subjects will provide 98% power to detect a mean difference of 2.0‰. Assuming SD to be 1.5‰ (at most) for the change in BDV before and after the diagnosis of an infection is made, a total sample size of 100 subjects and an infection rate of 5%, a mean decrease of 2.0‰ prior to and after the confirmed infection will be detected with 79% power at the one sided 5% significance level (secondary hypothesis).

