## 10. Rationale for any Deviation from Pre-specified Analysis Plan

Not applicable at this time.

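### The protocol and the SAP name different primary hypotheses, and a trial of up to 100 subjects cannot give the SAP's PCT non-inferiority tests their stated 80% power

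*SAP*

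**What the plan says.** **Protocol.** Section 2.1 gives the primary objective as "To define variation of BDV in critically ill adult subjects admitted to ICUs", with this hypothesis: "Null hypothesis: BDV in critically ill adult ICU subjects is equal to BDV in non-infected adult ICU subjects". Section 7.1 attaches the primary label to a different contrast. It says the mean BDV difference between subjects "diagnosed with a nosocomial infection and subjects not diagnosed with an infection is expected to be 2.0‰ or more (primary hypothesis". The sizing begins "Assuming that 5% of the subjects will have a confirmed nosocomial infection over the monitoring period and an overall standard deviation of 1.5"‰ and arrives at 100 subjects (5 infected, 95 not), at least 80% power, two-sided 5%. Section 3.0 caps enrolment at 100 from 8–10 centres, and section 7.1 raises the target to 110 to allow for losses. Section 3.0 also describes a pilot: "Effectiveness parameters will be estimated to determine the sample size required for the subsequent pivotal study".

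PCT is a planned comparator in the protocol. Daily blood is stored for it (Study Summary, General Study Design), and section 3.0 says BDV will be compared with it. It appears in no objective, aim or hypothesis in section 2. The one marker comparison listed as an objective there, in 2.3, is against SIRS/MEWS.

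**SAP.** Section 5 (Hypotheses) sets two co-primary endpoints. The first null is that "BDV sensitivity is more than 10% worse than PCT sensitivity for progression to severe sepsis and septic shock"; the second repeats this for specificity. Section 6 requires both to reach significance for the study to succeed, at one-sided 2.5% with a 10% margin, and plans 97 pairs for each with at least 80% power. Section 5 assumes that half the subjects are infected. The two-sample t-test of mean BDV stays in sections 6 and 9, without primary status.

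**The concern.** Each document is coherent if read alone. Read together, they give the same trial two primary hypotheses, which differ in:

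- **estimand:** a mean difference, against paired differences in sensitivity and specificity;
- **comparator:** non-infected subjects, against PCT;
- **target condition:** nosocomial infection, against progression to severe sepsis or septic shock;
- **error rate:** two-sided 5%, against one-sided 2.5%;
- **infected share:** 5%, against 50%;
- **size:** 100 subjects, against 97 + 97 pairs.

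The same data could meet one criterion and miss the other, and neither document says which decides. There is also a feasibility question. The SAP's tests need many infected subjects, while the protocol's size was chosen for a comparison that works with five.

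**Working it through.** **1. The protocol's figure reproduces.** Inputs from 7.1: difference 2.0‰, SD 1.5‰, 5 against 95, two-sided 5%. The standard error is 1.5 × √(1/5 + 1/95) = 0.688, so the noncentrality is 2.0/0.688 = 2.91 on 98 degrees of freedom. Power is 82.1% by noncentral t and 82.8% by the normal approximation, against at least 80% stated. With 10 against 90 it is 97.7% by noncentral t, against 98% stated.

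**2. The SAP's figure reproduces.** Inputs from SAP Table 1: expected difference 0.100, discordant proportion 0.400, limit −0.100, one-sided 2.5%, 97 pairs. The discordant cells are p10 = (0.400 + 0.100)/2 = 0.25 and p01 = (0.400 − 0.100)/2 = 0.15. The test used here is Tango's score test, z = (b − c + 0.10n)/√(n(2q − 0.11)). Here b and c are the discordant counts and q is the estimate of p01 restricted to p10 − p01 = −0.10. Non-inferiority is declared at z ≥ 1.96. Summing the multinomial probabilities of all outcomes that pass gives 88.1% at n = 97, against 89% in Table 1.

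Neither document has an arithmetic error here. Each is right for its own, different, primary.

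**3. The SAP's sensitivity test at the protocol's size.** Same method and Table 1 rates, counting infections as the events, in 100 subjects:

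| Infected share | Source | Infected pairs | Power |
|---|---|---|---|
| 5% | Protocol 7.1 sizing | 5 | 6.9% |
| 10% | Protocol 7.1 alternative | 10 | 15.1% |
| 18% | Top of the cited 6–18% range | 18 | 27.9% |
| 50% | SAP section 5 | 50 | about 61% |

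The specificity test must also pass, so the chance of overall success is no higher than these figures.

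**4. What very few pairs can show.** If BDV and PCT agreed on every infected subject (b = c = 0), the lower 97.5% bound with 5 pairs would be −43%. At least 35 pairs are needed before that bound clears −10%.

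**5. Subjects needed for 97 infected pairs.** 97/0.05 = 1,940; 97/0.10 = 970; 97/0.18 = 539 (rounded up); 97/0.50 = 194. The protocol provides up to 100, with 110 enrolled to allow for losses.

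**6. The 2.1 null.** Inclusion criterion 2 (section 3.1.1) makes every subject a critically ill ICU patient, so the non-infected are a subset of the first group named in 2.1. Let f be the infected fraction. The mean of all subjects minus the mean of the non-infected equals f × (infected mean − non-infected mean). For f > 0, that is zero exactly when infected and non-infected means are equal.

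**The case against.** **The SAP has its own infection rate.** Its 80% target belongs to 97 events and a 50% infected share, so quoting only the 5–18% results would be selective. This stands, and the 50% case is included above. It narrows the gap but does not close it: about 61% on sensitivity alone, and 194 subjects needed.

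**PCT is not foreign to the protocol.** This also stands. The comparison was planned; its primary status, its non-inferiority form and its role as the success rule are what the SAP adds.

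**Stronger readings a reader might infer, which the documents do not support:**

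- *That the 2.1 null is a third hypothesis with no test, or that the study would be powered against a diluted effect.* By step 6, that null is true exactly when infected equals non-infected, and protocol 7.2 tests this with the t-test and the mixed model. No analysis of all subjects against a subset is planned. What remains is a wording fault: the groups overlap, and the 2.0‰ effect does not describe that contrast.
- *That SAP section 10 denies any departure from the protocol.* Its entry is "Not applicable at this time", under a heading about deviations from the pre-specified analysis plan. It may be a placeholder for later departures from the SAP itself.
- *That the SAP lets the sponsor choose between primaries.* It does not; it fixes one success rule. The ambiguity lies between the documents, and nothing in them shows an intent to exploit it.
- *That the SAP was written for another version of the protocol.* Its eligibility criteria and BDV threshold also differ, which makes this possible, but neither document says so.

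**Conclusion.** The point holds and should be resolved before database lock. The two documents set different primary hypotheses, and neither gives precedence to one. The protocol's size supports its own 7.1 comparison (about 82% power). It does not support the SAP's stated 80%: the sensitivity test has between about 7% and 61% power as the infected share runs from 5% to 50%.

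These figures rest on three assumptions: Table 1's discordance rates, a score test standing in for the SAP's paired test (it matches Table 1 to within a point), and every infection counting as an event. The last is generous. The SAP's hypotheses concern severe sepsis or septic shock, while its sample-size text counts infections; if only the narrower condition qualifies, there are fewer pairs. The fault in 2.1 is a wording correction.

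**What to change.** State one primary hypothesis, one target condition, one infection-rate assumption and one sample-size basis, identically in both documents, before database lock. There are two routes.

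- **If the protocol's size of up to 100 governs:** make the 7.1 comparison primary in the SAP and report the BDV–PCT differences in sensitivity and specificity as estimates with 95% confidence intervals. Remove the rule that both PCT endpoints must be significant, and the 80% power statement for those tests.
- **If the PCT tests govern:** amend protocol sections 2.0 and 7.1 to match, and restate the power that the actual number of qualifying pairs provides.

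On either route, record in the SAP how its primary relates to, or changes from, the protocol's. Reword the 2.1 null as: BDV in infected subjects equals BDV in non-infected subjects.

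The cost is wording in two documents. The first route gives up a success claim that the trial cannot support at this size. The second keeps the claim but must state its lower power openly, or enrol about 194 subjects at 50% infected and more at lower rates.
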